11.4 Prior IGIV Therapy

Prior immunoglobulin G (IgG) therapy will be coded using WHO-DD (Version March 1, 2015). The number and percent of subjects who used different IgGs will be presented by ATC Levels 2 and 3, and the coded synonym.

11.5 Prior and Concomitant Medications

Prior and concomitant medications will be coded using WHO-DD (Version March 1, 2015). Prior medications are defined as those with a start date before the date of the first Subgam-VF infusion.

The number and percent of subjects taking prior and concomitant medications will be summarized by classification according to preferred term and route. If a subject has taken a prior/concomitant medication more than once, the subject will be counted only once in the respective total.

The number and percent of subjects taking pre-medications during the study will also be summarized by preferred term. These will be identified by a review of the coded medications.

12. EFFICACY ANALYSES

As this is a pharmacokinetic and safety study, no formal efficacy analyses are planned.

13. SAFETY ANALYSES

Safety data will be presented using the Intent-to-Treat population.

The variables used to assess safety will be the following:

- Drug exposure
- Adverse Events
 - The number and percent of adverse events (AEs) including infusion site reactions.

- The number and percent of infusions associated with one or more AEs that begin during the infusion, up to one hour, 24 hours, 48 hours or within 72 hours after completion of the infusion.
- Adverse reactions, defined as any AE occurring during the infusions or within 72 hours of the infusion completion OR any AE classed as product related.
- Thrombotic events
- Nature, severity, and frequency of AEs (tolerability)
- Suspected unexpected serious adverse reactions (SUSARs), if any
- Vital signs
- Clinical laboratory tests including tests for hemolysis
- Transmission of viruses
- Physical examination

13.1 Extent of Exposure

The duration of exposure will be expressed as the time in days from the first infusion of Subgam-VF through to the Follow-up visit at week 27 (inclusive). Duration will also be expressed categorically in months, where a month is defined as a calendar month.

The actual dose in mg/kg, based on the total volume infused and body weight, will also be calculated at each infusion.

Duration of infusion will also be summarized for each infusion. A summary of the number of subjects exposed and the total duration of exposure across all subjects will also be presented by infusion dose category (categories to be defined following review of data), age group and gender, and race.

13.2 Adverse Events (AEs)

Although all AEs will be listed, summary tables will be based on treatment emergent adverse events (TEAE), defined as those with onset between first infusion date and 28 days after the last infusion.

An overall summary of TEAEs will show the number and percent of subjects who report any TEAE, any study drug related TEAE, any serious TEAE, any study drug related serious TEAE, and any TEAE leading to discontinuation. The 2-sided 95% exact confidence intervals for the incidence in each of the categories will be calculated and expressed as a percent. Tables will be presented for the pediatric subgroups in addition to all subjects, all adults and all pediatric subjects.

The number and percent of infusions associated with one or more AEs (irrespective of causality) that occur during the infusion or within 72 hours after completion of the infusion will be calculated. A 1-sided 95% upper confidence bound for this percent will be derived. If the upper bound is less than 40%, excluding local infusion site reactions, the incidence of infusion-related AEs associated with Subgam-VF will be considered acceptable. In addition, the number and percent of subjects who report any AEs and the number and percent of subjects who report any AEs at least possibly related to Subgam-VF will be calculated, and the upper bound of the 95% confidence interval for the percentages will be presented. Tables will be presented for the pediatric subgroups in addition to all subjects, all adults and all pediatric subjects.

The overall incidence of TEAEs (number and percent of subjects reporting an event, and the number of events) will be summarized by system organ class (SOC) and preferred term (PT). This summary will be repeated showing only events occurring in ≥5% of all subjects.

The number and percent of subjects with TEAEs at each infusion will be presented by the most recent infusion number for each infusion schedule. These summaries will be by SOC and PT and will summarize all events, all product related events and all events not product related. Events will be associated with an infusion if they begin during the infusion or within 72 hours after the completion of the

infusion. Product related events include all events that were possible, probable or very likely/certain related to study drug.

The number and percent of subjects with product related TEAEs, and the corresponding number of events, will be summarized by SOC and PT.

The number and percent of subjects with AEs that occur during an infusion will be summarized overall and by the infusion rate at which the AEs are reported. If necessary, the infusion rate will be grouped into different levels. The number and percent of subjects with AEs that occur during an infusion will also be summarized by the number of infusion sites, and by the location of infusion (home or clinic).

In addition, the number and percent of subjects with AEs occurring within 1, 24, 48, 72 and over 72 hours after infusion completion will also be summarized by SOC and PT. This summary will be repeated for product related events.

The number and percent of subjects with AEs will be summarized by maximum intensity and strongest study drug relationship. If more than 1 AE is recorded for a subject within any SOC or PT, the subject will be counted only once at the worst severity or strongest relationship.

The number and percent of subjects with serious TEAEs and product related serious TEAEs will be summarized by SOC and PT. In addition, non-serious, product related TEAEs will also be summarized. Tables will be presented for the pediatric subgroups in addition to all subjects, all adults and all pediatric subjects.

The number and percent of subjects with suspected unexpected serious adverse reactions (SUSARs) will be summarized by SOC and PT. To assess 'expectedness', all AE will be reviewed to determine whether event meets the definition of "unexpected," based on whether the event is listed in the Investigator's Brochure. Unexpected AE will be identified prior to database lock for data summarization.

Listings will be provided for all AEs, AEs temporally associated with infusion (events beginning during the infusion or within 72 hours after the completion of the infusion), SAEs, SUSARs and AEs resulting in discontinuation.

Infusion site reactions will be listed and summarized. The Investigator will determine if these should be recorded as AEs. Infusion site reactions will be recorded as AEs when the symptoms/signs lead to infusion stop, require concomitant medication, or have an impact on the general condition of the subject as judged by the Investigator.

FDA Specified AE Table: The AE table as specified below will also be presented.

Adverse reactions are defined as treatment emergent adverse events which meet any of the following criteria:

- (a) adverse events which begin during an infusion of Subgam-VF or within 72 hours of the end of an infusion,
- (b) adverse events considered by the investigator to be possibly, probable, or very likely/certain related to administration of Subgam-VF,
- (c) adverse events for which the investigator's causality assessment was either missing or indeterminate. The above defined adverse reactions, sorted by preferred term based on Intent-to-Treat, will be summarized in two columns: 1) Number and percent of subjects experiencing the AE using total number of subject as denominator. 2) Number and percent of events using total number of infusion as denominator.

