# **Treatment Period (Weeks 1 to 26)**

• Eligible subjects then return seven days (+/- 1 day) after the Screening/Baseline visit for their first Subgam-VF dose (Week 1 visit). Weekly dosing will be administered for 26 weeks during which time safety will be assessed. Site visits (Weeks 1, 2, 5, 9,

Page 22 of 87

13, 17, 21, 22 and 26) – subjects will attend the clinic at specific points and they will receive their Subgam-VF infusion at the clinic. There will also be routine safety assessments, which will include blood sampling. After the Week 2 visit and if an appropriately qualified member of the study team or the subject's carer is available, then arrangements may be made to conduct some of the visits at the subject's home to reduce the number of visits to the sites. Alternatively a Home Health Agency may be utilized. The subject would be required to sign an IRB/EC approved consent form to permit the site to share the subject's details with the agency in order for them to collect the samples/conduct the assessments.

- If the subject is not already receiving IgG via the subcutaneous route, following training by the site during the preceding Subgam-VF visits it is planned that home infusions will begin on Week 3 (3rd infusion of Subgam-VF). For home infusions, subjects (or care givers) will infuse Subgam-VF themselves and will record any concomitant medications, date and time of any adverse events (including inspecting the infusion site for reactions) and record details of their Subgam-VF dose. If the subject requires further assistance this will be provided (i.e. it is not mandatory that these infusions are performed at home).
- There will be a telephone follow up by an appropriately qualified site staff member on day 3 after each site administered and home administered infusion to check for any adverse reactions including infusion site reactions and remind subjects to document these in their subject study diary. The date of infusion is considered to be Day 0. If Day 3 is to fall on a weekend or public holiday then this telephone follow up call should be performed on the closest working day after Day 3 as possible.

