## 7.2. Infusions

Subjects will receive 26 infusions of Subgam-VF subcutaneously on a weekly schedule using the supplied infusion pumps.

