# 13.4. Safety Analysis

#### 13.4.1. Adverse Events

Summaries of AEs will be based on treatment-emergent AEs (TEAEs), defined as those events with onset date between the first infusion date and 28 days after the last infusion.

The number and percent of infusions associated with one or more AEs (irrespective of causality) that occur during the infusion or within 72 hours after completion of the infusion will be calculated. A 1-sided 95% upper confidence bound for this percent will be derived. If the upper bound is less than 40%, excluding local infusion site reactions, the incidence of infusion-related AEs associated with Subgam-VF will be considered acceptable. In addition, the number and percent of subjects who report any AEs and the number and percent of subjects who report any AEs at least possibly related to Subgam-VF will be calculated, and the upper bound of the 95% confidence interval for the percentages will be presented. AEs occurring during the infusion and within 1, 24, 48 and 72 hours after the infusion completion will also be summarized.

An adverse reaction will be defined as any AE occurring during the infusion and within 72 hours after the infusion completion OR any AE classed as product-related or with unknown causality.

AEs that occur during an infusion will be summarized by the infusion rate at which the AEs are reported. If necessary, infusion rates will be grouped into different levels.

SAEs and SUSARs will be summarized with all AEs, and separate listings will be provided for SAEs and SUSARs.

All other safety assessments will be summarized descriptively for each treatment group.

Further summaries of AEs will be detailed in the Statistical Analysis Plan.

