10. GENERAL ISSUES FOR STATISTICAL ANALYSES

Subject listings of all data represented in the electronic CRF (eCRF) will be provided. Measurements from subjects excluded from the predefined analysis populations or extra measurements (such as unscheduled or repeat assessments) will not be included in summary tables unless specified otherwise, but will be included in the subject listings. In general, the subject listings will be sorted by subject number and assessment date (and time) if applicable.

Unless otherwise specified, descriptive statistics will include the number of subjects with data to be summarized (n), mean, standard deviation (SD), median, minimum and maximum. The same number of decimal places as in the raw data will be presented when reporting minimum and maximum, 1 more decimal place than in the raw data will be presented when reporting mean and median, and 2 more decimal places than in the raw data will be presented when reporting SD.

All categorical/qualitative data will be presented using absolute counts and percentages. The total number of subjects in the treatment group overall (N) will be used as the denominator for percentage calculations, unless stated otherwise in the table shell. All percentages will be presented as one-decimal point, unless otherwise specified. Percentages equal to 100 will be presented as 100% and percentages will not be presented for zero frequencies.

All analyses and summaries will be produced using SAS® version 9.2 (or higher).

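### AEs during infusion by rate, number of sites and location are reported as percent of subjects, which mixes tolerability with the number of infusions given in each category

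*SAP*

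**What the plan says.** For rate, SAP 13.2 states: "The number and percent of subjects with AEs that occur during an infusion will be summarized overall and by the infusion rate". The next sentence covers site number and home or clinic location: the "number and percent of subjects with AEs that occur during an infusion will also be summarized by the number of infusion sites". The unit is the subject in all three tables.

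SAP 10 sets the default denominator: "The total number of subjects in the treatment group overall (N) will be used as the denominator for percentage calculations". A table shell may override this, but the shells are not in the documents.

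Protocol 13.4.1 says only that "AEs that occur during an infusion will be summarized by the infusion rate at which the AEs are reported". It names no unit and no denominator.

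Elsewhere the SAP does work with infusions:
- The 40% acceptability criterion in SAP 13.2 is a percent of infusions, presented overall and by age group.
- The FDA-specified table in the same section relates events to total infusions, by preferred term.
- SAP 6.2 and 13 list the percent of infusions with AEs, including AEs that begin during the infusion, as a safety variable.

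None of these is split by rate, site number or location. SAP 13.1 breaks exposure down by dose category, age group, gender and race, and not by these three factors.

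**The concern.** One subject can contribute infusions at more than one rate, with more than one site count, and both in clinic and at home. A subject counts as a case in a category after one AE there, so the chance of being counted grows with the number of infusions received in that category. Those numbers are unequal by design.

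A reader will use these tables to ask whether faster rates, more sites or home self-infusion are less well tolerated. On a subject basis, the category with more infusions can look worse when the risk per infusion is the same. A real excess in the category with fewer infusions can be masked. If the default denominator applies, subjects who never had an infusion in a category also dilute its percentage.

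**Working it through.** **Inputs from the documents**
- Infusions per subject: "Subjects will receive 26 infusions of Subgam-VF subcutaneously on a weekly schedule" (Protocol 7.2).
- Clinic infusions: the list in Protocol 7.1 starts "Site visits (Weeks 1, 2, 5, 9" and continues with 13, 17, 21, 22 and 26. At these visits "they will receive their Subgam-VF infusion at the clinic".
- Home infusions: "it is planned that home infusions will begin on Week 3" (Protocol 7.1) for subjects new to the subcutaneous route. Home infusion is not compulsory.
- Rate: 20 mL/hr/site at the first infusion, then up to 30 (Protocol 8.2.3, SAP 5.2).
- Site number: a maximum of six at once, or eight for subjects of at least 100 kg. The number of infusions per site count is not stated.

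**Reproducing the plan's count.** Clinic weeks number 9. The other weeks (3–4, 6–8, 10–12, 14–16, 18–20, 23–25) number 2 + 3 + 3 + 3 + 3 + 3 = 17. The total is 9 + 17 = 26, as stated.

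**Assumption.** The documents give no AE risk per infusion. I take a risk p that is equal in every category, from 1% to 10%.

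**Independent infusions.** P(at least one AE in m infusions) = 1 − (1 − p)^m. For example, at p = 5%: clinic 1 − 0.95^9 = 37.0%; home 1 − 0.95^17 = 58.2%.

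| p | Clinic (9) | Home (17) | First (1) | Later (25) |
|---|---|---|---|---|
| 1% | 8.6% | 15.7% | 1.0% | 22.2% |
| 2% | 16.6% | 29.1% | 2.0% | 39.7% |
| 5% | 37.0% | 58.2% | 5.0% | 72.3% |
| 10% | 61.3% | 83.3% | 10.0% | 92.8% |

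The last two columns are an extreme case in which every subject runs above the first rate from infusion 2 onward.

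**Within-subject correlation.** With a beta-binomial model and correlation ρ, P(no AE in m) = B(a, b + m)/B(a, b), where a = p(1/ρ − 1) and b = (1 − p)(1/ρ − 1). At p = 5%:

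| ρ | Clinic (9) | Home (17) | First (1) | Later (25) |
|---|---|---|---|---|
| 0.05 | 31.9% | 46.8% | 5.0% | 56.2% |
| 0.10 | 28.2% | 39.5% | 5.0% | 46.5% |
| 0.30 | 18.9% | 23.9% | 5.0% | 27.0% |

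The gap shrinks but does not close.

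**Masking.** Under independence, the two locations show the same subject percentage when clinic risk = 1 − (1 − home risk)^(17/9). A home risk of 5% then matches a clinic risk of 9.2%, a ratio of 1.85. Over home risks of 2% to 10% the ratio is 1.87 to 1.80.

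**With infusions as the unit.** Equal risk gives equal expected percentages, for example 5% in clinic and 5% at home. For 30 subjects completing the nominal schedule the denominators are 30 × 9 = 270 clinic and 30 × 17 = 510 home infusions, and 30 first and 30 × 25 = 750 later infusions.

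**The case against.** The case for leaving the tables alone has real content.

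- **Status.** The tables are descriptive, with no test or decision rule. The one pre-specified safety criterion, the 40% bound, already uses infusions. This stands.
- **Partial cover elsewhere.** SAP 13.2 also plans the percent of subjects with TEAEs at each infusion number. Each subject contributes one infusion there, so infusion 1 can be compared with later ones on equal exposure. A reader might infer that an excess at the first infusion would go unseen, and the plan does not support that. The cover is only partial: that table includes the 72 hours after infusion and is not split by actual rate, site number or location.
- **Denominator.** A reader might infer that all subjects will certainly be the denominator. It is only the default, and a shell may change it. Changing to exposed subjects would remove the dilution but not the accumulation over repeated infusions.
- **Size.** The 9/17 split is nominal, because home infusion is optional and some visits may take place at home. The 1/25 split needs universal escalation, whereas 30 mL/hr/site is a maximum and lower rates are allowed. At 1% risk and 30 subjects, clinic against home is about 3 against 5 subjects (30 × 0.086 and 30 × 0.157). These limits affect the size of the distortion and not its direction.
- **Protocol.** Protocol 13.4.1 is not at fault. It fixes no unit, and an infusion-based table would satisfy it.
- **Confounding.** An infusion denominator does not give a clean comparison. Rate depends on earlier tolerability, increases are first tried in clinic, and home AEs come from diaries and telephone calls. This stands and should be stated with the tables.

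**Conclusion.** The point holds as a fault in how three descriptive tables are built. Percent of subjects with at least one AE is not comparable across rate, site-number or location categories, because it combines tolerability with the number of infusions. No planned table gives per-infusion percentages for these three splits.

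For location, equal risk per infusion yields 8.6% against 15.7% at an assumed 1% and 37.0% against 58.2% at 5% under independence. At 5% with correlation 0.30 it yields 18.9% against 23.9%. The rate contrast can be larger but depends on how many subjects escalate. For site number the direction and size cannot be calculated, because no distribution is given. All these figures rest on assumed risks and on the nominal schedule.

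A reader might conclude that the tables show exposure and nothing about tolerability. That goes too far, since they carry both. The 40% rule and the PK analysis are not touched.

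**What to change.** In SAP 13.2 and the matching shells, for each rate, site-number and location category:

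1. Report the infusions given, the infusions with at least one AE during the infusion, and the percent of infusions.
2. If a subject count is kept, use as denominator the subjects with at least one infusion in that category, and show that number.
3. Make any confidence interval allow for repeated infusions within a subject.
4. State how an infusion is classified if its rate was reduced after an AE, which Protocol 7.11 provides for.
5. Add a note that the comparisons remain confounded, for the reasons given above.

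The cost is shell and programming work. Protocol 7.18 already has subjects record rate and sites for each home infusion, so no new data should be needed. One small drawback is that a few subjects with repeated AEs can dominate an infusion percentage. Showing the infusion and subject counts side by side makes that visible.

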13.3 Vital Signs

Vital signs tables will show summaries for all ages combined, all pediatrics (2 to 15 years of age) and adults (16 years and over).

Descriptive statistics for vital signs (absolute values and change from baseline) will be presented for each study visit. Descriptive statistics for percent change from pre-infusion value will be presented at each of the post-infusion measurements for the following vital signs: blood pressure (diastolic and systolic), pulse rate, respiration rate and temperature. Since each subject has multiple infusions throughout the study,

the average change over all infusions for each subject will first be calculated, so that the descriptive statistics will summarize the mean change over all infusions for each subject. The pre-infusion value at each infusion will be the average of the measurements recorded at 10 minutes prior to infusion, and at infusion start.

13.4 Clinical Laboratory Evaluations, Tests for Markers of Hemolysis and Viral Transmission Tests

All summaries of laboratory data will be based on the Intent-to-Treat population. Tables will be subset for all pediatrics (2 to 15 years of age) and adults (16 years and over). Tables will also show summaries for all ages combined.

Descriptive statistics and change from baseline values will be provided for biochemistry and hematology results at each visit. The baseline value for each parameter is defined as the last result prior to the first infusion (usually collected on Day 1).

Summaries of urinalysis will be split by type of result: continuous or categorical. For categorical results (e.g., dipstick tests), the table will display the number and percent of subjects with the given result at the specified visit. Continuous results will be summarized as described above for biochemistry and hematology.

Results of tests for markers of hemolysis (Direct Coombs' test, haptoglobin, plasma free haemoglobin and urine hemoseridin) will be summarized by the number and percent of subjects with the given result at each visit. Percentages will be based on the number of subjects in the ITT population for the given infusion schedule. Two additional listings will be produced:

- 1) showing all the above values, and those for serum bilirubin and LDH, for visits in which at least one of the parameters is indicative of hemolysis.
- 2) showing absolute haemoglobin, change from baseline, and Direct Coombs' tests at each visit

Viral transmission test results will be summarized as described above for the markers of hemolysis test results. In addition, a shift table will show changes from baseline to end of study for each test. The shift table will be subset by age only and percentages will be calculated from the number of subjects with the given result at baseline.

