## 7.11. Vital Signs

Vital signs assessed by qualified personnel will be entered on the eCRF. The vital signs to be observed will be:

- diastolic blood pressure (mmHg)
- systolic blood pressure (mmHg)
- pulse rate (beats/min)
- respiration rate (breaths/min)
- temperature (°C)

## Page 30 of 87

The subject must be in the same position each time vital signs are obtained. Temperature must be recorded using the same method every time e.g. orally, under the arm or via another common method.

Any clinically significant changes in vital signs will be reported as AEs as described in Section 10.2.

Clinically significant hypotension and/or anaphylactic reactions (significant hypotension with generalized hives/angioedema or bronchospasm) warrant discontinuation of the infusion and administration of appropriate supportive care as deemed necessary by the investigator (this may include: epinephrine, antihistamine, corticosteroids, supplemental oxygen, expansion of the plasma volume as necessary, etc.). These occurrences must be recorded on the eCRF as AEs. At the discretion of the investigator, the subject may be withdrawn from the study, but will complete the follow-up visits.

If a subject has been assessed as being dehydrated and is given intravenous fluids before beginning the subcutaneous study infusion, the baseline vital signs will be taken after the rehydration fluids have been given but before infusion of investigational product.

Vital signs will be recorded once during the screening and follow up visits.

Vital signs will be recorded during site visits at the following times:

- 10 minutes before the start of each Subgam-VF infusion (+/- 5 minutes)
- 30 minutes after stopping the Subgam-VF infusion (+/- 15 minutes)

Vital signs are also an important safety variable.

If any AE of moderate or severe intensity occurs, the rate of the infusion at which this AE occurred will be recorded, and the infusion rate will be reduced appropriately, depending upon the severity of the AE symptoms. The infusion may then be resumed at a rate tolerated by the subject. Also see the most current Subgam-VF Investigator Brochure (IB) for a list of common product-related AEs.

Before listing changes in vital signs as AEs, each change should be assessed for clinical relevance.

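### SAP 13.3's only pre-to-post-infusion vital-sign summary averages percent change over all of a subject's infusions, diluting a single-infusion change about ninefold, and its pre-infusion value needs a reading nobody schedules

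*SAP*

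**What the plan says.** SAP 13.3 plans two kinds of vital-sign summary. The first gives absolute values and change from baseline by study visit. Baseline, under SAP 10.1, is the last value before the first infusion of study drug.

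The second looks at change around the infusion itself: "Descriptive statistics for percent change from pre-infusion value will be presented at each of the post-infusion measurements", for "blood pressure (diastolic and systolic), pulse rate, respiration rate and temperature". Because subjects have many infusions, "the average change over all infusions for each subject will first be calculated", and the descriptive statistics are then taken over these subject averages. The starting point is defined as follows: "The pre-infusion value at each infusion will be the average of the measurements recorded at 10 minutes prior to infusion, and at infusion start".

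The protocol's reading times are in section 7.11. At site infusions there are two: "10 minutes before the start of each Subgam-VF infusion (+/- 5 minutes") and "30 minutes after stopping the Subgam-VF infusion (+/- 15 minutes"). The vital-signs footnotes to protocol Table 2 and to SAP Table 1 give the same two times. Section 7.11 records temperature in °C.

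Three general rules also matter. SAP 10 includes the minimum and maximum among the default statistics and lists all eCRF data by subject. SAP 10.2 allows no imputation of missing data. Protocol 7.11 has clinically significant vital-sign changes reported as AEs.

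**The concern.** Readings are paired around an infusion to pick up acute effects, and an acute effect belongs to one infusion. A subject's average over all infusions is a poor measure of it: one large change is spread over the uneventful infusions, and a fall at one infusion cancels a rise at another. Subjects with fewer infusions are diluted less, so the extremes of the averages are not comparable between subjects.

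Two further problems are independent of the averaging. The stated pre-infusion value needs a reading that is not scheduled, so the rule cannot be applied as written. Percent change in temperature depends on where the scale puts its zero, which for °C is arbitrary.

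What is at stake is the usefulness of a safety table. Safety is a secondary objective, protocol 4.2 reports no clinical trial data for this product, and SAP 10.7 plans no data safety monitoring board.

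**Working it through.** The plan states no figure on this point, so there is none to reproduce. The sizes of the events below are illustrative assumptions.

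**1. Infusions with paired readings.** Protocol 7.1 and Table 2 place site infusions at Weeks 1, 2, 5, 9, 13, 17, 21, 22 and 26. That is 9 of the 26 infusions.

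**2. Dilution.** If the percent change is d at one infusion and zero at the others, and k infusions have readings, the subject's value in the table is d / k.

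- 30% systolic fall, k = 9: -30 / 9 = -3.3%. In a mean over 30 subjects (the protocol's target number of evaluable subjects) this is -3.3 / 30 = -0.11 percentage points.
- Systolic 120 to 80 mmHg: -40 / 120 = -33.3%. With k = 9 the subject's value is -3.7%, with k = 5 it is -6.7%, and with k = 2 it is -16.7%.

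**3. Whether the minimum and maximum recover the event.** They are extremes of subject averages. A simulation of 30 subjects with 9 infusions each, 4,000 runs per row, gave one subject the 33.3% fall at one infusion. All other changes were normal with mean zero and an assumed SD. The table shows how often the affected subject was the tabulated minimum.

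| Assumed SD of change (percentage points) | SAP averaging | Change shown by infusion visit |
|---|---|---|
| 5 | 57% | 100% |
| 8 | 29% | 99.9% |
| 12 | 15% | 92% |

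Even where the affected subject is the minimum under averaging, the value shown is near -3.7%, not -33.3%.

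**4. Whether the by-visit tables recover it.** They measure change from study baseline, not from that infusion's pre-dose value. The SAP does not say whether they use the pre- or the post-infusion reading.

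**5. The pre-infusion value.** SAP 13.3 requires the "average of the measurements recorded at 10 minutes prior to infusion, and at infusion start". Protocol 7.11, the protocol Table 2 footnote and the SAP Table 1 footnote schedule one reading before the infusion and one after it. With no imputation, the SAP's value is either undefined or becomes the 10-minute reading alone, and the SAP does not say which. The reference to several post-infusion measurements does not fit a schedule with one. The SAP cites protocol version 5.0 and the protocol reviewed is version 6, but the SAP's own footnote has the same two readings, so the conflict lies within the SAP.

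**6. Temperature.** A rise from 37 to 39 °C is 2 / 37 = +5.4%. The same rise in °F, from 98.6 to 102.2, is 3.6 / 98.6 = +3.7%. Averaged over nine infusions, the °C figure becomes 5.4 / 9 = +0.6%.

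**The case against.** A reader might infer four stronger things, and the documents support none of them.

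- *That the reaction disappears.* It is reduced to 1/k, not removed, and the subject's raw values remain in the listings. The factor of nine applies to a completer; a subject who withdraws after a reaction has a smaller k. Averaging across subjects is ordinary for a summary mean and is not a second defect.
- *That this is the only analysis of infusion effects.* It is the only pre-to-post summary of vital signs. SAP 13.2 plans the share of infusions with an AE up to 72 hours after the end, judged against 40%. It also plans AEs by infusion number, by rate, by number of sites, by location and by time window, a listing of temporally associated AEs, and adverse reactions counted against infusions. None of these averages within subject. Protocol 7.11 sends clinically significant changes, hypotension included, into the AE record.
- *That the unscheduled reading hides reactions.* It does not. The dilution comes from the averaging; the missing reading is a separate mismatch.
- *That temperature results could differ by unit in this trial.* The protocol fixes °C. The Fahrenheit figure shows only that the percentage has no fixed meaning.

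It is also fair to say that neither document requires the table to act as an independent check on AE reporting, that it can cover only 9 of 26 infusions, and that no decision rests on it.

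This limits the consequence but does not answer the point. The AE route depends on a judgment of clinical significance, listings are not a summary, and the by-visit tables use a different reference value. The pre-infusion rule still cannot be applied as written.

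**Conclusion.** The point holds as a defect of safety reporting. The only pre-to-post vital-sign summary dilutes a change at one infusion about ninefold for a completer, so a 30% systolic fall appears as -3.3% for that subject, and its minimum and maximum do not reliably reveal the event. The ninefold figure assumes nine infusions with readings and no change at the other eight. The simulated detection rates rest on assumed SDs of 5 to 12 percentage points.

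Separately, and without any assumption, the pre-infusion value calls for a reading that neither document schedules, and percent change is the wrong scale for temperature in °C.

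The event itself remains in the listings and, if judged clinically significant, in the AE tables. The primary PK analysis and the 40% safety criterion do not change.

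**What to change.** In SAP 13.3:

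- Define the pre-infusion value as the scheduled reading 10 minutes before the start, and refer to a single post-infusion reading.
- Report temperature as absolute change in °C.
- Keep the subject-level mean if wanted. Alongside it, show pre-to-post change by infusion visit, or each subject's largest fall and largest rise over the clinic infusions.
- With either, give the number and percent of clinic infusions beyond limits that the sponsor fixes before database lock.
- State whether the by-visit tables use the pre- or the post-infusion reading.

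The cost is SAP wording and one extra descriptive table. The scheduled readings already supply the data.
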